#### 9.1.8 Athens Insomnia Scale (AIS)

The severity of sleep disturbance will be self-assessed daily starting from baseline using the Athens Insomnia Scale (AIS).

The AIS is a self-administered psychometric instrument consisting of eight items (Appendix 11). The first five items of the AIS (assessing difficulty with sleep induction, awakenings during the night, early morning awakening, total sleep time, and overall quality of sleep) correspond to Criterion A for the diagnosis of insomnia according to ICD-10 (International Statistical Classification of Diseases and Related Health Problems 10th Revision), while the requirements of a minimum frequency (at least three times a week) and duration (1 month) of any complaint correspond to Criterion B of the ICD-10. The ICD-10 requirements of marked distress caused by the sleep problem and/or interference with ordinary activities of daily living (Criterion C) are covered through the strictly subjective nature of the response options for every item of the scale as well as through the content of the last three items pertaining to the next day consequences of insomnia (problems with sense of well-being, functioning, and sleepiness during the day).

Each item of the AIS can be rated 0-3 as detailed in Appendix 9.

The responders are requested to rate positively if they had experienced the sleep difficulty described in each item at least three times a week between the study visits (Soldatos *et al.* 2000).

### 9.1.9 Patient Oriented SCORAD (PO-SCORAD)

The PO-SCORAD will be measured at each clinic visit, except the screening visit. The PO-SCORAD is the SCORAD completed by the patients themselves. It is a self-evaluation tool developed by the European Task Force on Atopic Dermatitis (2011). Six items (erythema, edema/papulation, oozing/crusts, excoriation, lichenification, and dryness) will be selected to evaluate the AD severity. The overall surface affected, loss of sleep and pruritus will also be evaluated by patients on a visual analog scale. The detailed procedure of PO-SCORAD is provided in Appendix 10.

## 9.2 Safety Assessments

### 9.2.1 Medical / Surgical History

A complete review of the patient's medical history will be undertaken by the Investigator or designee at the Screening Visit (Visit 1) to ensure that no exclusion criteria have been met. Any concomitant disease, whether considered relevant for the study or not by the Investigator, must be reported in the CRF. The date of diagnosis or duration of the condition should be noted where possible.

### 9.2.2 Physical Examination

A physical examination will be performed by the Investigator as per the Study Flow Chart (Appendix 1) in accordance with local practices. This examination will be symptom-directed, i.e., a standard panel of body systems will not be assessed unless indicated by patient. For example should the patient report to the Investigator the presence of 'rash' then the skin would be evaluated. It is not required that additional body systems are assessed unless clinically warranted. Any clinically significant abnormal results should be recorded in the CRF. Changes in findings of the physical examination compared with the baseline examination should be recorded as an AE.

### 9.2.3 Vital Signs

Vital sign measurements will be performed as per the Study Flow Chart (Appendix 1). Measurements to be taken include:

- Blood pressure: will be performed as supine (after at least 5 minutes of rest) systolic and diastolic blood pressure (in mmHg)
- Heart rate: taken at rest (in bpm)
- Temperature: will be taken as per clinic practice. Temperature and route will be recorded in the CRF.

Vital signs measurements will be performed before any blood samples are taken. All new findings or changes to previous findings considered clinically significant will be recorded in the CRF as an AE if the finding is made after the patient has signed the ICF.

### 9.2.4 Clinical Laboratory Safety Tests: Haematology and Serum Biochemistry

Blood samples will be taken as per the Study Flow Chart (Appendix 1) for routine haematology and serum biochemistry tests. All samples will be analysed in the central laboratory.

**Table 2: Clinical Laboratory Safety Tests**

Haematology:	Full blood count to include red cell count, haemoglobin, haematocrit, white cell count, differential white cell count, platelet count and reticulocyte count.
Serum biochemistry:	Urea (blood urea nitrogen; BUN), creatinine, uric acid, total bilirubin, potassium, , alkaline phosphatase (ALP), aspartate aminotransferase (AST), alanine aminotransferase (ALT), lactate dehydrogenase (LDH), creatine phosphokinase (CPK), albumin, total protein, cholesterol, triglycerides, glucose.

If required a Follicle-Stimulating Hormone (FSH) test to confirm non-child bearing potential will be carried out at screening only.

Details of the volume of blood to be taken, sample preparation and handling are contained in a separate Laboratory Procedures Manual. Laboratory results will be reviewed for clinically significant values by each Investigator following sample analysis and verification. The report must be signed and dated by the Investigator before insertion in the CRF.

Additional blood may be required for repeats of safety laboratory test.

### 9.2.5 Pregnancy Test

For female patients of childbearing potential, a pregnancy test will be carried out at screening and Week 16/Visit 7/ET Visit, as per the Study Flow Chart (Appendix 1).

### 9.2.6 Virology

A blood sample will be taken to perform virology tests including human immunodeficiency virus (HIV), Hepatitis C and Hepatitis B at screening as detailed in Study Flow Chart (Appendix 1).

### 9.2.7 Electrocardiogram (ECG)

A 12-lead ECG 10 mm/1 mv, 25 mm/s with a 10 second lead II rhythm strip will be recorded on the days indicated in Study Flow Chart (Appendix 1). Patients will be rested quietly in a fully supine position for 5 minutes before the ECG is taken.

Use of a 6-lead ECG is acceptable if no 12-lead ECG is available.

### 9.2.8 Body Mass Index (BMI)

Weight (kg) and height (cm) will be collected to calculate the BMI (kg/m^2), and will be recorded at Screening/Visit 1 and Week 16/Visit 7/Early Termination (ET). The height will only be recorded once at the screening visit and the same value will be used for BMI calculation at Week 16/Visit 7/ET visits.

### 9.2.9 DGLA Plasma Concentration Sampling

Blood samples for trough total DGLA plasma concentration analysis will be collected via direct venepuncture as per the Study Flow Chart (Appendix 1).

The detailed instruction for DGLA plasma sample collection, processing, storage and shipment will be provided in a separate procedure.

### 9.2.10 Biomarker Sampling

Blood samples will be collected via direct venepuncture as per the Study Flow Chart (Appendix 1). The samples will be stored for the potential analysis of AD biomarkers at a later date.

The detailed instruction for biomarker sample collection, processing, storage and shipment will be provided in a separate procedure.

### 9.2.11 Sample Storage, Handling and Shipping

Sample storage, handling and shipping will be done as per standard operating procedures and as specified in the Laboratory Procedures Manual.

### 9.2.12 Adverse Event Assessment

See Section 11.

### 9.2.13 Concomitant Medication

Any medication (prescription as well as over the counter (OTC) drugs, vitamins and antacids) or therapeutic intervention deemed necessary for the patient, and which, in the opinion of the Investigator, do not interfere with the safety and efficacy evaluations, may be continued unless they are included in the list of ‘medications and therapeutic regimens excluded from the study’ outlined below. However, the Investigator should be cautious in evaluating the need for change in dosage and should carefully assess if any concomitant medication is necessary.

Any medications, herbal medicines, natural health remedies and nutritional supplements used within 30 days prior to Screening (Visit 1) until completion (Visit 8) are to be recorded in the concomitant medication module in the CRF system. The generic name of the medication (i.e., not local trade names), along with start date, stop date, dose, route, regimen and indication shall be recorded as applicable in the CRF system.

Any new medications or changes to the dose or regimen of pre-existing medications will be updated on a routine basis during the study.

Investigational new drugs (i.e. drugs that are not marketed in the local market) should not be co-administered with the IMPs during the entire period of the study.

#### 9.2.13.1 Permitted Therapies

##### 9.2.13.1.1 Emollients

All patients should be applying bland emollient, **initiated at least 7 days prior to Baseline/Day 0**, usually twice a day on their skin including AD lesions. Emollient use must continue at the same frequency and on the same skin areas throughout the study. Any change in the frequency, application of the skin area or the emollient by the patient must be documented in the patient’s compliance log. Patients will be asked to avoid using emollients containing any active ingredient which has or may have an effect on AD including the following ingredients:

- Urea
- Ceramide
- Hyaluronic acid

**Note:**

*Patients who have been on a stable emollient with an active ingredient (for example urea, ceramide and hyaluronic acid) for at least 12 weeks prior to screening and are otherwise*

*eligible may continue using their pre-existing emollients, if deemed appropriate by the investigator and if they are willing and able to continue using the same stable emollient for the duration of the study*

Every effort should be made to use the same emollient throughout the study. The commercial name of the selected emollient(s) will be recorded in the source document and the eCRF, along with the frequency and quantity. Patients will also record on a daily basis their emollient use as instructed by the clinic staff. No other products may be applied to the lesions during the study. On the day of the visit, patients should apply emollient after all assessments have taken place.

#### **9.2.13.1.2 Other Permitted Therapies**

Non-sedative anti-histamines (e.g. loratadine, fexofenadine) are allowed during the study only if used to treat medical conditions other than AD. Such medications are allowed during the study only if the patient has been on a stable dose for at least 4 weeks prior to Baseline/Day 0 and continues to use the same agent everyday throughout the study.

Inhaled and intranasal corticosteroids for stable medical conditions are allowed.

#### **9.2.13.2 Medications and therapeutic regimens excluded from use in the study**

The following topical therapies or procedures are prohibited during the study for all patients:

- Topical medicated treatments that could affect AD, including but not limited to:
  - topical corticosteroids
  - tars
- Any topical product containing urea, ceramides or hyaluronic acid
- Systemic therapy that could affect AD, e.g. retinoids, methotrexate, cyclosporine, hydroxycarbamide (hydroxyurea), azathioprine and oral/injectable corticosteroids
- Any biological agent
- UV-A or UV-B phototherapy
- Psoralen + Ultraviolet A (PUVA) therapy
- Use of tanning booth
- Any other investigational medicinal product
- Traditional medicine, herbal extracts and supplements used to treat AD

#### **9.2.14 Restrictions**

##### **Behavioural**

Patients will be asked to refrain from any travel to sunny climates or use of tanning equipment, saunas and swimming throughout the duration of the study.

Extensive UV exposure or UV-B devices will be prohibited within 4 weeks of the start of the trial and during the trial.

##### **Other**

Patients will be instructed to abstain from using any drugs/treatments that may influence AD (refer to exclusion criteria and prohibited therapies or procedures section) throughout the study.

Patients will be required to administer the drug 2 hours after the consumption of food. Medication(s) for other conditions that are permitted in the study can be taken as usual. Patients will also be instructed to not consume food for approximately 1 hour after IMP administration.

### 9.2.15 Rescue Treatment

If medically necessary (ie, to control intolerable AD symptoms), rescue treatment for AD may be provided to study patients at the discretion of the investigator. If possible, investigators should avoid administration of rescue treatments before Week 4 due to the expected time to onset of treatment-response following DS107 treatment.

For the purpose of efficacy analysis, patients who receive rescue treatment during the study treatment period will be considered treatment failures from the time rescue treatment is used.

Topical corticosteroids or calcineurin inhibitors may be used for rescue, but should be reserved for problem areas only, eg, face, neck, intertriginous and genital areas, etc. If a patient receives rescue treatment with systemic corticosteroids or non-steroidal systemic immunosuppressive drugs (cyclosporine, methotrexate, mycophenolate mofetil, azathioprine, etc.) study treatment will be immediately discontinued.

Investigators should make every attempt to conduct efficacy and safety assessments (eg, disease severity scores, safety labs) immediately before administering any rescue treatment.

## 10 INVESTIGATIONAL MEDICINAL PRODUCT / INVESTIGATIONAL DRUG

### 10.1 Investigational Medicinal Product (IMP)

The following medication supplies will be used in the study:

#### DS107 capsules:

Each DS107 capsule contains 500mg DGLA as an active ingredient in an opaque, oval soft gelatin capsule.

#### Placebo capsule:

Each matching placebo capsule contains 500mg of liquid paraffin in an opaque oval soft gelatin capsule.

### 10.2 Supply, Packaging, Labelling, Handling and Storage

DS107 capsules will be provided by the Sponsor as opaque, oval soft gelatin capsules containing 500mg of DGLA.

Placebo capsules will also be provided by the Sponsor as opaque, oval soft gelatin capsules containing 500mg of liquid paraffin.

DS107 capsules will be supplied in manufactured form (blinded), packaged in cold formed aluminium foil blisters of 28 units. Placebo will be presented in identical blisters and packs and stored/packaged the same as DS107 capsules. Study medication will be labelled according to EU and US regulations.

The study medication will be provided by the Sponsor to the Investigator and will be kept, on site, in a locked room or cabinet with limited access. DS107 and placebo capsules should be stored at a controlled room temperature between 15-25°C and will only be supplied to patients in the trial under the supervision of the Investigator.

[figure not shown]
### 10.3 Dosage and Administration

This study involves a comparison of DS107 (2g) with placebo, administered orally once daily for a total duration of 16 weeks. **The last study drug administration should occur on the day preceding Week 16 (Visit 6) / Early Termination (ET) visit.** Patients will be randomized to one of the two treatment groups in a 1:1 ratio:

- 2g DS107 (4 DS107 capsules) administered once-daily for 16 weeks
- Placebo (4 placebo capsules) orally administered once-daily for 16 weeks

Patients will be required to administer the drug 2 hours after the consumption of food. Medication(s) for other conditions that are permitted in the study can be taken as usual. Patients will be also be instructed to not consume food for approximately 1 hour after IMP administration. On the day of the visit, patients should take dose after all assessments have taken place.

B blister packs will consist of 7 rows of 4 capsules with each weekday detailed. Each row constitutes one dose. Patients will be instructed to take the 4 capsules **from left to right**, on the relevant day, as shown below:

To maintain the blind throughout the study, the DS107 capsules and placebo capsules will be identical in appearance.

#### 10.4 Duration of Treatment

Patients will be orally administered DS107 or placebo once daily for 16 consecutive weeks.

#### 10.5 Methods for Assigning Patients to Treatments

Approximately 220 patients will be randomized into double-blind treatment groups in a 1:1 ratio by an Interactive Web Response System (IWRS) as follows:

- 2g DS107 (4 DS107 capsules) administered once daily for 16 weeks
- Placebo (4 placebo capsules) orally administered once daily for 16 weeks

A randomization list permuted by blocks and stratified by site will be generated by the Sponsor or its designee. The randomization schedule with study drug assignments will be generated prior to the start of the study and will be known only to the individuals responsible for labelling the study drug, the statisticians generating the schedule and the IWRS team responsible for implementing the schedule. The IWRS will assign a medication kit number to each patient and the contents will be based on the randomization code.

At the investigational site, each patient will be assigned a patient identifier number during screening that will be used on all patient documentation. The patient identifier number will contain the site number and the patient number assigned in numerical order at the screening visit (e.g.: 102-10 for the tenth patient screened at the site number 02). Patient numbers will be assigned in ascending order starting with 01.

#### 10.6 Drug Accountability

All IMP supplies for this study must be retained in a safe place at all times of the study. Only personnel authorised by the principal Investigator at each site should dispense the IMP and the

accountability is the responsibility of the Investigator. The Investigator or pharmacist must complete the IMP supply form, verifying the receipt of IMP. The patients should return all used and unused packs of IMP to the study site at every visit. Following compliance assessment the packs of IMP will be retained in a secure location at the site until the end of the study. After the Clinical Research Associate (CRA) has completed a final drug accountability review, the IMP may be returned or destroyed only when instructed by the CRA.

## 11 ADVERSE EVENTS AND SERIOUS ADVERSE EVENTS

### 11.1 Definitions of Adverse Events

#### 11.1.1 Seriousness

##### *Adverse Events (AE):*

Any undesirable experience occurring to a patient that has signed the ICF and who has taken their first dose of the study drug, whether or not considered related to the investigational IMP(s). All AEs must be recorded in the case report form, defining relationship to IMP and severity. AEs should also be recorded by the Investigator in the patient file/notes.

##### *Serious Adverse Events (SAE):*

If a patient experiences a serious adverse event after the first dose of the study drug, the event will be recorded as a serious adverse event.

*A serious adverse event (experience) or reaction is any untoward medical occurrence that at any dose:*

- results in death
- is life-threatening
- requires in-patient hospitalization or prolongation of existing hospitalization
- results in persistent or significant disability/incapacity, or
- is a congenital anomaly/birth defect

Note: The term "life-threatening" in the definition of "serious" refers to an event in which the patient was at risk of death at the time of the event. It does not refer to an event which hypothetically might have caused death if it were more severe.

Medical and scientific judgment should be exercised in deciding whether expedited reporting is appropriate in other situations, such as important medical events that may not be immediately life-threatening or result in death or hospitalization but may jeopardize the patient or may require intervention to prevent one of the other outcomes listed in the definition above. These should also usually be considered serious.

Examples of such events are intensive treatment in an emergency room or at home for allergic bronchospasm, blood dyscrasias or convulsions that do not result in hospitalization, or development of drug dependency or drug abuse.

##### *Unexpected Adverse Event (UAE):*

An experience not previously reported in the Investigator's Brochure or similar product information sheet such as the Summary of Products Characteristics (SPC).

#### 11.1.2 Severity

The intensity of an AE is an estimate of the relative severity of the event made by the Investigator based on his or her clinical experience. The following definitions are to be used to rate the severity of an AE:

- Mild: The adverse event is transient and easily tolerated.
- Moderate: The adverse event causes the patient discomfort and interrupts the patient's usual activities.

- **Severe:** The adverse event causes considerable interference with the patient's usual activities, and may be incapacitating or life-threatening.

### 11.1.3 Relationship to IMP

The Investigator will establish causality of the AE to experimental treatment. The Investigator should take into account the patient's history, most recent physical examination findings, and concomitant medications.

The following definitions will be used to determine causality of an AE:

- **Not related:** temporal relationship of the onset of the AE, relative to the experimental treatment is not reasonable or another cause can explain the occurrence of the AE.
- **Related:** temporal relationship of the onset of the AE, relative to the experimental treatment is reasonable, follows a known response pattern to the treatment, and an alternative cause is unlikely.

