### 11.1.4 Reporting of AEs and SAEs

All AEs must be recorded in the case report form, defining relationship to IMP and severity. The frequency of each AE should always be recorded to indicate if the event is intermittent, continuous, one-time event etc. If the same AE occurs repeatedly at approximately the same strength in the same patient, this AE should be counted only once. If any aspect of the AE changes (including but not limited to severity, frequency, causality), a new AE should be recorded. AE start and end dates should be clearly defined in the CRF.

**As soon as the Investigator is aware of a potential SAE, he/she should report the SAE to the Pharmacovigilance (PV) CRO by fax or e-mail, and in any case no later than 24 hours after the knowledge of such a case. In case of questions regarding an SAE, the investigator or authorized study personnel can contact the PV CRO monitor by phone. The contact information, is provided in the Investigator Site File.**

At the time of the call, the Investigator must provide as a minimum requirement, the Patient number, birth date, nature of the SAE, and a preliminary assessment of causality. The Investigator should follow-up the initial notification of the potential SAE by faxing/e-mailing a copy of the form to PV CRO at the number/address provided in the Investigator Site File. The SAE reporting form should be received to the PV CRO within 24 hours after knowledge of such a case.

Follow-up information on an existing SAE that is fatal or life-threatening should be reported by the Investigator to PV CRO within 5 days after the initial report. Where appropriate, hospitalisation or autopsy reports should be made available. All SAEs will be followed up until resolution (i.e., asymptomatic, stabilisation or death).

AE's should be reported for the entire study duration up to and including the follow up period. Following completion of the study, if the Investigator becomes aware of any AE that is potentially related to the IMP, the Sponsor should be notified.

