## 11.2 Serious Adverse Reactions and Unexpected Adverse Reactions

### 11.2.1 Definitions

#### **Adverse Reaction:**

All noxious and unintended responses to a medicinal product related to any dose should be considered adverse drug reactions.

The phrase "responses to a medicinal product" means that a causal relationship between a medicinal product and an adverse event is at least a reasonable possibility i.e. the relationship cannot be ruled out.

For marketed medicinal products, an adverse reaction is a response to a drug which is noxious and unintended and which occurs at doses normally used in man for prophylaxis, diagnosis, or therapy of disease or for modification of physiological function.

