***Unexpected Adverse Reaction:***

An adverse reaction, the nature or severity of which is not consistent with the applicable product information (e.g. Investigator's Brochure for an unauthorised investigational product or similar product information sheet such as the Summary of Products Characteristics (SPC)).

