***Suspected Unexpected Serious Adverse Reaction (SUSAR):***

Any serious adverse reaction that might be related to the IMP and are unexpected according to the definition above.

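### The causality categories in Protocol 11.1.3 contradict the adverse-reaction standard in 11.2.1 and leave an event of a new kind unclassifiable

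*Protocol*

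**What the plan says.** Protocol 11.1.3 introduces its scale with "The following definitions will be used to determine causality of an AE" and offers two levels. 'Related' joins three conditions: the onset "relative to the experimental treatment is reasonable, follows a known response pattern to the treatment, and an alternative cause is unlikely". 'Not related' needs only one of two: the timing "is not reasonable or another cause can explain the occurrence of the AE". There is no third level.

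Protocol 11.2.1 defines an adverse reaction more broadly. It is enough that a causal relationship "is at least a reasonable possibility i.e. the relationship cannot be ruled out". Expectedness is a separate test: a reaction is unexpected if it is one "the nature or severity of which is not consistent with the applicable product information". A SUSAR is then "Any serious adverse reaction that might be related to the IMP and are unexpected according to the definition above".

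The rating is used throughout. Section 11.1.4 states "All AEs must be recorded in the case report form, defining relationship to IMP and severity", and the first SAE call must include a preliminary view on causality. Protocol 12.7 tabulates AEs by relationship. SAP 7.5 makes related AEs a category of their own, reported in table 14.3.2.4 and listing 16.2.7.3.

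**The concern.** A causality scale should ask whether the drug may have caused the event. Whether events of that kind have been seen before is the expectedness question, which 11.2.1 already handles separately. Section 11.1.3 puts familiarity inside causality, so an event of a new kind fails 'Related' because it is new.

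The second limb raises a different problem. If some other cause could account for the event, 11.1.3 makes it Not related, even where the drug is also plausible and cannot be excluded. Under 11.2.1 the same event would count as a suspected reaction.

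At stake is what the trial can say about drug-related toxicity. Treatment lasts 16 weeks, against 8 weeks in both earlier oral studies in patients (Protocol Table 1). Gastrointestinal events, the most common AEs with DS107 in the Phase 1 and Phase 2a studies, fit a known pattern and can be rated Related. An effect that first appears with longer treatment cannot, on the literal wording.

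**Working it through.** The plan states no figure on this point, so the check is logical. Three yes/no conditions are taken from 11.1.3:

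- T: timing is reasonable
- K: the event follows a known response pattern
- C: another cause can explain the event

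One assumption is needed: an unlikely alternative cause is read as not-C. The two rules are then:

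- Related = T and K and not-C
- Not related = not-T or C

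Three conditions give 2 × 2 × 2 = 8 combinations.

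| T | K | C | Combinations | Result under 11.1.3 |
|---|---|---|---|---|
| no | either | either | 4 | Not related |
| yes | either | yes | 2 | Not related |
| yes | yes | no | 1 | Related |
| yes | no | no | 1 | Neither |

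Totals: Related 1, Not related 4 + 2 = 6, neither 1; 1 + 6 + 1 = 8.

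**Last row against 11.2.1.** The timing fits, nothing else explains the event, and it is of a new kind. Under 11.2.1 the relationship could hardly be ruled out, so the event would count as an adverse reaction. If its nature is not in the product information it is unexpected, and if it is also serious it meets the SUSAR definition. Section 11.1.3 has no category for it.

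**Second row against 11.2.1.** A competing explanation does not by itself rule the drug out. Section 11.1.3 settles both combinations as Not related. Section 11.2.1 leaves them open and, where the drug remains a reasonable possibility, counts them as reactions.

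**Effect of dropping K alone.** Related becomes T and not-C, which is 2 combinations. Not related stays at 6, and neither falls to 0. The gap closes, but the two combinations in the second row are still decided against the drug automatically. Aligning with 11.2.1 therefore needs both limbs changed.

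**Sensitivity to the assumption.** If an alternative cause can be capable of explaining an event and still be unlikely, some known-pattern events meet both definitions at once. The gap for a new kind of event with no other cause remains under either reading.

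**Outputs that depend on the rating:** the investigator's preliminary causality on each SAE, the tabulation by relationship in Protocol 12.7, SAP table 14.3.2.4 and listing 16.2.7.3.

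**Outputs that do not:** the incidence of TEAEs and SAEs, which is the secondary safety endpoint (Protocol 5.2), and SAP tables 14.3.2.2, 14.3.2.3 and 14.3.2.6 to 14.3.2.8.

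**Search for a repair.** Neither document gives another causality scale, qualifies the known-pattern condition, or describes a second causality assessment by the sponsor or the pharmacovigilance CRO. Protocol 7.5, 7.8 and 12.8.4 add to the mismatch: they speak of possible and probable attribution, levels that a two-level scale does not supply.

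**The case against.** A reader might infer that literal use of 11.1.3 would produce no SUSARs at all, that a new serious event leaves the expedited route, and so that the SUSAR definition is defeated. The documents do not support any of these.

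- Under 11.2.1 an event can be unexpected in severity alone. Such an event may follow a known pattern, be rated Related and be a SUSAR. The block applies only to events new in nature.
- Section 11.1.4 sends every potential SAE to the pharmacovigilance CRO within 24 hours, whatever its causality. Section 11.2.2 gives SUSAR reporting to that CRO, and the SUSAR definition does not refer back to 11.1.3. Nothing says that a Not related rating ends the assessment.
- Read strictly, the new event is not Not related either. How a site would resolve the gap is not stated.

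Two further points have some weight. First, 11.1.3 does not define a known response pattern and does not equate it with listing in the Investigator's Brochure, so a lenient reading would shrink the affected group. Second, the weight given to an alternative cause is a threshold choice on which sponsors may differ.

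These points limit the consequences but do not remove the conflict. The lenient reading is not written down, and the protocol has chosen two different thresholds in adjacent sections. Routing SAEs to the CRO does nothing for non-serious AEs or for the related-AE outputs.

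**Conclusion.** The concern holds as an internal contradiction. Section 11.1.3 cannot classify an event of a new kind with reasonable timing and no other cause, and its alternative-cause limb is stricter than the standard in 11.2.1. The investigator's rating, the only causality assessment the protocol describes, and the related-AE outputs are affected.

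The size can be stated only logically: one of eight combinations has no category, and two more are settled as Not related where 11.2.1 may disagree. The combinations are not equally likely, and the documents give no event rates from which to estimate patients. Undercounting of new toxicities in table 14.3.2.4 and listing 16.2.7.3 is possible but not certain. It occurs if sites resolve the gap as Not related or leave the field blank, or if the alternative-cause limb is applied as written. A new toxicity would still appear in the all-AE and SAE comparisons between arms. No sample size or efficacy result changes.

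The conclusion rests on the plain conjunctive reading of 'Related', and on there being no overriding causality instruction in documents outside the protocol and SAP, such as the SAE form or the CRO's procedures.

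**What to change.** Rewrite 11.1.3 to use the standard already in 11.2.1:

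- Related: there is a reasonable possibility that the IMP caused the event, meaning that the relationship cannot be ruled out.
- Not related: there is no such reasonable possibility.

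Drop the known-pattern condition, which belongs to expectedness. Make clear that a possible alternative cause does not by itself make an event Not related. Put the same definition in the eCRF completion guidance, so that table 14.3.2.4 and listing 16.2.7.3 rest on it. Reconcile the possible and probable attribution wording in Protocol 7.5, 7.8 and 12.8.4 with the chosen scale; the discontinuation and stopping rules themselves are not at issue here.

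The cost is a wording change in the protocol and in the eCRF guidance. Somewhat more AEs will be rated related in both arms, and more may be assessed for expedited reporting.
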